## 9.2.2.2. Day 7 and Day 14 (Phone Checks, +/- 1 day)

The site will call the patient on Day 7 and Day 14 to assess for any adverse events or tolerability issues the patient may have experienced since starting dosing. A review of systems will be discussed and any changes in concomitant medications will also be solicited.

- If a patient reports satisfactory tolerability to study medication on the Day 7 Safety Check-in, they will be instructed to increase their morning dose to 3 tablets and their evening dose to 3 tablets.
- If a patient reports tolerability issues, an additional week of dosing with the morning dose of 1 tablet and evening dose of 1 tablet may be performed.
- Patients who are unable to tolerate even the single tablet after 2 weeks of dosing are to be discontinued from the study.

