#### 10.3. Patient Withdrawal Criteria

The intent of this study is to follow all subjects until study termination unless the subject withdraws consent. Patients will be informed that they have the right to withdraw from the study

at any time for any reason without prejudice to their medical care. The Investigator also has the right to withdraw patients from the study if it is in their best interest. Patients may be withdrawn from the study if they:

- Have entered the study in violation of the protocol
- Require use of a prohibited concomitant medication
- Experience an AE that warrants premature withdrawal

All treated patients should be followed according to the Schedule of Assessments. All patients, even those who are withdrawn prematurely, should have all evaluations for the Month 12/ET Visit performed, if possible. All procedures required should be documented in the electronic case report form (eCRF). For all patients who withdraw prematurely, the Investigator will indicate one of the following reasons for withdrawal on the eCRF:

- Adverse event (AE)
- Death
- Protocol violation
- Lost to follow-up
- Patient's decision
- Other (reason to be specified by the Investigator)

In case of patients' withdrawal from the study due to an AE, such patients will be closely monitored until the resolution or stabilization of the AE. The Investigator should document the reason for withdrawal in the source documentation and eCRF.

If a patient withdraws participation from the trial early, early withdrawal should be documented by the Investigator (or designee) in the appropriate eCRF pages and source documents when confirmed.

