#### 12.5. Administration

All patients will take PCS499 300 mg BID with food for 1 week. Beginning at Week 2, patients will commence administration of twice daily dosing of three PCS499 300 mg tablets (900 mg BID) with food. Patients will continue at their assigned dose for the remainder of the study.

Safety and tolerability will be assessed throughout study and the following steps may be taken:

• During the dosing period, if a patient receiving PCS499 900 mg BID experiences unacceptable toxicity (i.e., non-transient, moderate to severe limitation in activity) that is deemed by the Investigator to be related to study drug, his/her dose will be changed to PCS499 600 mg TID with food at the discretion of the Investigator in consultation with the Medical Monitor. If this dose is not tolerated, the dose will be further reduced to PCS499 600 mg BID with food at the discretion of the Investigator in consultation with the Medical Monitor. If 4 out of the first 6 patients dosed in this study require dose modification or discontinue from the study due to a drug-related adverse event within 1 month of dosing, consideration will be made to change the starting dose to 600 mg TID with food for all subsequent patients. If clinically indicated at any time during the study, study medication will be discontinued. However, patients will not be discontinued from the study due to cessation of study drug.

All changes in medication administration will also be noted in the eCRF.

Each kit will be clearly marked with dosage instructions.

Each subject's medication will be packaged for dispensing as described in the study manual.

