#### 19.5.2. Patient Discontinuation

If a patient is discontinued from the study prematurely, the Investigator must select a reason for discontinuation on the termination page (End of Study Phase Status) eCRF. In addition, every effort should be made to complete the assessments listed under the early termination study visit. Patients withdrawn from the study will be considered evaluable for analysis.

A patient may be removed from the study for the following medical or administrative reasons:

- Adverse Event: If a patient experiences an adverse event that the patient finds unacceptable or that, in the judgment of the Principal Investigator, Processa Pharmaceuticals, Inc., or the Medical Monitor presents an unacceptable consequence or risk to the patient, the patient may be discontinued from further participation in the study.
- Administrative Discontinuation: After consultation with the Sponsor or Medical Monitor, a patient may be discontinued from the study for failure to comply with protocol requirements. All instances of noncompliance must be documented in the eCRF.
- Refusal of Treatment: If for any reason the patient refuses treatment during the study, the patient shall be discontinued from the study and the reasons for refusal documented on the eCRF. Reasonable efforts shall be made to monitor the patient for adverse events following such discontinuation. Such efforts shall be documented on the eCRF.

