### **2.9.1. Adverse Events**

Adverse events (AEs) will be coded using the Medical Dictionary for Regulatory Activities (MedDRA) version 21.1.

AEs occurring on or before Visit 2/Day 0 (Baseline) prior to drug administration will be regarded as “pre-treatment” and will not be included in the treatment emergent AE tabulations.

Treatment Emergent Adverse Events (TEAEs) are defined as any AE that starts or increases in severity after drug administration at Visit 2/Day 0 and will be summarized.

Listings of all AEs will be provided and separately by:

- Treatment Emergent AEs
- AEs leading to discontinuation of study
- Serious AEs

An overall summary table will be provided showing the number and percentage of patients with any:

- Pre-Treatment AEs
- TEAE
- Severe TEAE
- Serious TEAE
- Drug-related TEAE
- Drug-related severe TEAE
- Drug-related serious TEAE
- TEAE leading to withdrawal of study drug
- TEAE leading to change in study drug dose
- TEAE with outcome death

The number of reported AEs will also be shown in this summary table.

Summary tables for the following will also be presented:

- Summary of TEAEs by Body System and Preferred term,

- Summary of TEAEs by Severity,
  - If a patient has reported the same treatment emergent adverse event multiple times then the adverse event with the highest severity will be summarized.
- Summary of Drug-related TEAEs, and
- Summary of Drug-related TEAEs by Severity.
  - If a patient has reported the same drug-related treatment emergent adverse event multiple times, then the adverse event with the highest severity will be summarized.

Inferential statistical analysis comparing the AE data between active and placebo is not planned.

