### 3. Data Listing Shells

#### 3.1. Data Listings Table of Contents

The following post-text listings will be generated.

Listing Number	Listing Title
16.2.1	Patient Completion / Discontinuation
16.2.2	Protocol Deviations
16.2.3	Population Definitions
16.2.4.1	Demographics and Baseline Characteristics
16.2.4.2	Patient Eligibility and Informed Consent
16.2.4.3	Medical/Surgical/Procedural History
16.2.4.4	Necrobiosis Lipoidica History
16.2.4.5.1	Reference Lesion History
16.2.4.5.2	Reference Ulcer History
16.2.4.6	Non-drug Treatment History
16.2.4.7	Prior and Concomitant Medications
16.2.4.9	Safety Check In
16.2.5	Treatment Compliance
16.2.6.1.1	Reference Lesion Measurement Results
16.2.6.1.2	Reference Ulcer Measurement Results
16.2.6.1.3	Additional Lesion and Ulcer Reporting Results
16.2.6.2.1	Investigator Global Assessment: Necrobiosis Lipoidica Reference Lesion (IGA:NL) Results
16.2.6.2.2	Color and Ulcer Scale Reference Lesion (NLCUS) Results
16.2.6.2.3	Global Assessment Results
16.2.6.3.1	Dermatology Life Quality Index Results
16.2.6.3.2	Skindex-29 - Dermatology Survey Results
16.2.6.4	Biomarkers
16.2.6.5	Reference Lesion and Ulcer Photography
16.2.7.1	Adverse Events
16.2.7.2	Adverse Events Leading to Discontinuation of Study
16.2.7.3	Serious Adverse Events

Listing Number	Listing Title
16.2.8.1	Safety Laboratory Results - Hematology
16.2.8.2	Safety Laboratory Results - Chemistry
16.2.8.3	Safety Laboratory Results - Urinalysis
16.2.8.4	Safety Laboratory Results - Infectious Serology
16.2.9.1	Vital Sign Results
16.2.9.2	Physical Examination Results
16.2.9.3	Electrocardiogram Results

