14.2.06.1	Summary of Color and Ulcer Scale Reference Lesion (NLCUS) Results – Modified Intention-to-Treat Population
14.2.06.2	Summary of Color and Ulcer Scale Reference Lesion (NLCUS) Results – Per Protocol Population
14.2.07.1	Summary of Global Assessment Results – Modified Intention-to-Treat Population
14.2.07.2	Summary of Global Assessment Results – Per Protocol Population
14.2.08.1	Summary of Dermatology Life Quality Index Results – Modified Intention-to-Treat Population
14.2.08.2	Summary of Dermatology Life Quality Index Results – Per Protocol Population
14.2.09.1	Summary of Skindex-29 - Dermatology Survey Results – Modified Intention-to-Treat Population
14.2.09.2	Summary of Skindex-29 - Dermatology Survey Results – Per Protocol Population
14.2.10	Summary of Biomarker Results – Biomarker Population
14.3.1.1	Overall Summary of Adverse Events – Safety Population
14.3.1.2	Summary of Treatment Emergent Adverse Events by Body System and Preferred Term – Safety Population
14.3.1.3	Summary of Treatment Emergent Adverse Events by Body System, Preferred Term and Severity – Safety Population
14.3.1.4	Summary of Treatment Emergent Adverse Events by Body System, Preferred Term and Relationship to Study Medication – Safety Population
14.3.1.5	Summary of Adverse Events Leading to Study Discontinuation – Safety Population
14.3.1.6	Summary of Serious Adverse Events – Safety Population
14.3.5.1	Summary of Laboratory Results - Hematology – Safety Population
14.3.5.2	Summary of Laboratory Results - Chemistry – Safety Population

Table Number	Table Title
14.3.5.3	Summary of Laboratory Results - Urinalysis – Safety Population
14.3.6.1	Summary of Vital Signs Results – Safety Population
14.3.6.2	Summary of Electrocardiogram Results – Safety Population

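### Protocol 12.5 and 9.2.2.2 disagree on whether a tolerability stop ends study participation, and the SAP's discontinuation-specific AE outputs are worded for leaving the study, not for stopping drug

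*Protocol*

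**What the plan says.** On retention:

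- Protocol 12.5, in a list of safety and tolerability steps, allows study drug to be stopped at any time if clinically indicated and continues: "However, patients will not be discontinued from the study due to cessation of study drug". SAP 1.2 repeats the sentence.
- Protocol 10.3: "The intent of this study is to follow all subjects until study termination unless the subject withdraws consent".
- Protocol 9.2.2.2: "Patients who are unable to tolerate even the single tablet after 2 weeks of dosing are to be discontinued from the study".
- Protocol 19.5.2, on refusal of treatment: "If for any reason the patient refuses treatment during the study, the patient shall be discontinued from the study".
- Protocol 15.1.4.1 removes a patient whose pregnancy is confirmed by serum test.
- Protocol 9.2.3.3 sets a clinic visit for patients who stop drug before the study ends, so it treats stopping drug and leaving the study as separate events.

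On reporting:

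- The overall AE table in SAP 2.9.1 has a row for "TEAE leading to withdrawal of study drug" and none for leaving the study.
- The same section plans a separate listing of "AEs leading to discontinuation of study". Listing 16.2.7.2 ("Adverse Events Leading to Discontinuation of Study") and Table 14.3.1.5 ("Summary of Adverse Events Leading to Study Discontinuation") use the same event.
- Protocol 17.5.1 plans narratives for SAEs and for patients who leave the study because of a drug-related AE.
- SAP 2.3 summarises study entry, discontinuation and completion. It names no treatment disposition.

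**The concern.** Safety and tolerability is the only primary objective. In an uncontrolled study of about 12 patients, which adverse events made patients stop drug is a central tolerability result.

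Two things can go wrong. First, about 4 centers are planned. Sites that follow different sections could keep or remove the same patient after an early tolerability stop, which would change that patient's follow-up and disposition. Second, the more faithfully 12.5 is followed, the less the discontinuation outputs show. A patient kept in the study after an AE stopped treatment has not left the study, so outputs selected on study exit do not pick that patient up. The overall table and Table 14.3.1.5 would then describe different patients.

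**Working it through.** The documents give no sample size or power figure to reproduce. The check is a comparison of texts, followed by a simple size.

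**Step 1: do the retention rules cover the same patient?**

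| Section | Trigger | Effect on study participation | Force |
|---|---|---|---|
| Protocol 12.5, SAP 1.2 | Study drug stops; read in place, at least clinically indicated stops | Stays | Mandatory |
| Protocol 10.3 | Any, short of withdrawn consent | Followed to study end | Statement of intent |
| Protocol 9.2.2.2 | Cannot tolerate one tablet after two weeks | Leaves | Mandatory |
| Protocol 19.5.2, refusal | Patient refuses treatment | Leaves | Mandatory |
| Protocol 19.5.2, adverse event | Unacceptable AE | May leave | Permissive |
| Protocol 15.1.4.1 | Confirmed pregnancy | Leaves | Mandatory, specific |

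A patient who cannot tolerate the single tablet is a tolerability stop. That falls naturally within 12.5, which deals with tolerability and applies throughout the study. So 12.5 and 9.2.2.2 give opposite mandatory instructions for one patient. The refusal bullet is different: refusal is the patient's own act rather than a clinically indicated stop, so its tension is with the intent in 10.3. The adverse-event bullet is permissive and contradicts nothing.

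**Step 2: trace one patient through the outputs.** Take a patient who stops drug for a non-serious, drug-related TEAE and stays in the study.

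| Output | Event named | This patient |
|---|---|---|
| Overall AE table, drug-withdrawal row (SAP 2.9.1) | Drug stop | Counted |
| Tables 14.3.1.2 to 14.3.1.4 | TEAEs by body system and preferred term | Event present; title gives no link to the stop |
| Listing 16.2.7.1 | All AEs | Event present; link visible if drug action is shown |
| Listing 16.2.7.2 | Study exit | Absent |
| Table 14.3.1.5 | Study exit | Absent |
| Narratives (Protocol 17.5.1) | SAE, or study exit for a related AE | Absent |
| Disposition (SAP 2.3) | Study entry, exit, completion | Not counted as discontinued |

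The overall AE table has 10 patient-count rows: 1 for drug withdrawal and 0 for study discontinuation.

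**Step 3: size.** Let *d* be patients with an AE that stopped drug, *r* those of them kept in the study, and *x* patients who left the study for an AE with some other drug action recorded. The overall row shows *d*. Table 14.3.1.5 shows *d* − *r* + *x*. The gap is *r* − *x*. With *x* = 0 and N = 12:

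- *r* = 1: 1/12 = 8.3 percentage points
- *r* = 2: 2/12 = 16.7
- *r* = 3: 3/12 = 25.0

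The documents give no value for *r*, so no probability is attached to the gap.

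**The case against.** **A specific rule overrides a general one.** Section 9.2.2.2 could be read as an exception to 12.5, as the pregnancy rule can. That is a reasonable way to resolve the texts, but the protocol does not say so. Both 9.2.2.2 and 12.5 deal with tolerability, 12.5 is not limited by time, and the SAP repeats it without exception. The pregnancy rule concerns a different trigger and needs only a cross-reference.

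**The safety data are largely collected either way.** Section 9.2.3.3 sets a full assessment when drug stops. Section 10.3 asks for the Month 12/ET evaluations after withdrawal and follows AE withdrawals to resolution or stabilisation. Section 19.5.2 asks for reasonable efforts to monitor AEs after refusal. This stands, and it limits the harm.

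**The link can be recovered.** Protocol 15.2.1 records study drug action for each AE, and SAP 3.2 says all data will be listed. Listing 16.2.7.1 should therefore show which AE stopped drug, and with about 12 patients a reader can find it. This also stands. What remains is that the outputs meant to answer the discontinuation question would omit the patient.

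**Stronger readings that the documents do not support.**

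- A reader might infer that the by-term AE tables in general depend on study exit. Only Tables 14.3.1.2 to 14.3.1.4 are titled by term, and they depend on neither event. The title of Table 14.3.1.5 does not state a term breakdown.
- A reader might set 12.5 and the refusal bullet in 19.5.2 against each other as a direct contradiction. Their triggers differ.
- A reader might take a probability from the earlier Phase 2 study (Protocol 7.3.1). There, 4 patients stopped for a GI event in an arm of 89 (implied by 12 = 13.5%, 9 = 10.1% and 6 = 6.7%). That is 4/89 = 4.5%, so 1 − (85/89)^12 = 42% for at least one in 12. This covers GI stops only, at 600 mg BID, and says nothing about retention afterwards. It is not the chance of the mismatch described here.

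**Conclusion.** The concern holds in two limited parts. Protocol 9.2.2.2 conflicts with 12.5 and SAP 1.2 for a patient who cannot tolerate the single tablet, and no stated exception resolves it. The tension between 19.5.2 (refusal) and 10.3 is weaker. Separately, an AE that stops drug in a retained patient is missing from every discontinuation-specific table, listing, non-serious narrative and disposition count, although it is counted in the overall AE table. Each such patient is 8.3 percentage points of 12.

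The event is misplaced rather than lost: it stays in the general TEAE tables and should be traceable in the full listing. The reporting part assumes that the outputs select on the event in their titles and that at least one patient stops drug for an AE and stays. The shells are in a separate file (SAP 4.4), so selection and layout cannot be confirmed. The retention conflict does not depend on the shells. Severity is minor to should-fix.

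**What to change.** **Protocol.** The sponsor should reconcile 9.2.2.2, 12.5 (with SAP 1.2), 10.3 and the refusal bullet of 19.5.2, and cross-reference 15.1.4.1. Which retention rule applies is for the sponsor's clinical team; none is proposed here.

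**SAP.**

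1. Keep the study-discontinuation outputs, but widen Table 14.3.1.5, Listing 16.2.7.2 and the narrative criterion to AEs that led to drug withdrawal *or* study exit, with a separate flag for each. Adding a matching drug-withdrawal table and listing would serve as well. Selecting on drug withdrawal alone would not, because it drops the *x* patients of Step 3, who left the study for an AE with some other drug action recorded.
2. In disposition, report treatment discontinuation separately from study discontinuation.

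**Cost.** A wording clarification in the protocol, matching narrative wording in Protocol 17.5.1, and a small amount of extra programming. No new data are needed, because study drug action is already recorded for each AE (Protocol 15.2.1) and the existing drug-withdrawal row already requires that information.

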## 7.5. Study Rationale

No approved therapies exist for NL. Current treatment approaches are based on empirical evidence, but generally produce unsatisfactory results. These include corticosteroids (topical,

intralesional, and systemic), topical calcineurin inhibitors, anti-platelet agents, various immunosuppressants (chloroquine, thalidomide, TNF-α blockers, etc.), UV phototherapy, and skin grafting. For ulcerated lesions, wound care involving moisture control, infection control, conservative debridement, and compression therapy is employed. Spontaneous resolution has been reported in 13-19% of patients after 6-12 years (Muller, 1966).

Clinically, multiple case reports have been published suggesting benefit from the use of pentoxifylline (PTX) in NL patients, possibly related to its vascular and anti-inflammatory effects (Littler, 1987; Noz, 1993; Basaria, 2003; Wee, 2017). PCS499 is an analog of pentoxifylline that provides an exposure profile of active molecules more favorable to inhibiting the secretion of TNF-α, IFN-γ, and other pro-inflammatory cytokines. Furthermore, PCS499 has been well tolerated in Phase 1 studies at higher doses, which may be due to the flatter slope in achieving maximum plasma concentrations (Cmax) of active metabolites, which would be consistent with published reports that equate a higher rate of adverse events with a rapid drug absorption rate and higher maximum plasma concentrations for PTX (Cleary, 1999). Thus, PCS499 may benefit NL patients based on its enhanced inhibition of cytokines (TNF-α, IFN-γ) that induce inflammation and granuloma formation as well as its effect on red blood cell deformability and promotion of platelet deaggregation, which can improve microcirculatory flow. Furthermore, higher doses of PCS499 can be administered with resulting higher exposures of active molecules with no observed increase in adverse effects.

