### 10.2. Patient Exclusion Criteria

Patients will not be eligible for entry into this study if they meet any of the following exclusion criteria:

- 1. Current or previous (within 4 weeks of Baseline) treatment with:
  - a. Oral, topical, or intralesional corticosteroids;

- Date: 02 November 2018
- b. Systemic pentoxifylline, theophylline, or cilostazol
- c. Oral or topical retinoid;
- d. Other systemic or topical immunosuppressant drugs, including but not limited to calcineurin inhibitors (e.g., tacrolimus), thalidomide, apremilast, anti-malarials (e.g., hydroxychloroquine, chloroquine), cyclosporine, mycophenolate mofetil, azathioprine, methotrexate, etc.
- 2. Current or previous (within 12 weeks of Baseline) treatment with any biologic therapy (e.g., adalimumab, etanercept, infliximab, anakinra, etc.).
- 3. Phototherapy/photochemotherapy (NBUVB, UVB, PUVA) within 6 weeks prior to Baseline
- 4. Skin grafting, or other surgical procedure (other than debridement) within 6 weeks prior to Baseline.
- 5. History of drug allergy, including but not limited to pentoxifylline or other xanthine derivatives, or other allergy, which in the opinion of the Investigator, contraindicates participation.
- 6. Anticipated concurrent use of a strong CYP1A2 inhibiting drug, including but not limited to cimetidine and/or fluvoxamine, during the course of the study (after Screening).
- 7. Fever (>38°C), or chronic, persistent, or recurring infection(s) at Screening or Baseline.
- 8. Any infection requiring oral antimicrobial therapy within 2 weeks prior to Baseline or any infection requiring parenteral antibiotics or hospitalization within 12 weeks prior to Baseline. Any treatment for such infections must have been completed and the infection cured for at least 2 weeks prior to Baseline.
- 9. History of sarcoidosis, pyoderma gangrenosum, or any other disorder (in the judgment of the Investigator) that would interfere with the evaluation of NL or require protocol prohibited medication.
- 10. History of any life threatening infection or sepsis within 12 months of Baseline:
- 11. Clinically significant cardiac disease including but not limited to unstable angina, acute myocardial infarction within 6 months of Baseline, and arrhythmia requiring therapy.
- 12. Patient has QTc interval ≥ 480 milliseconds on Screening ECG; a second Screening ECG may be done at investigator's discretion but the average of the two QTc screening intervals must not be ≥ 480 milliseconds.

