#### 11.2. Concomitant Medications

At the discretion of the Investigator, over-the-counter (OTC) medications will be allowed for the management of a self-limiting indication (e.g., acetaminophen for headache). The use of concomitant OTC medications, including OTC herbals, must be approved by the Investigator before administration. All prescription medications must be approved by the Investigator throughout the active treatment period.

With the exception of PCS499, investigational drugs are not to be taken during the study.

IMPORTANT: Patients should be instructed to consult with the Investigator before taking any new medication or changing medications and/or dosing regimens throughout the study.

Drugs that are known to be strong inhibitors of CYP1A2 may increase exposure to the investigational product. The Investigator should contact the Medical Monitor prior to (if possible) the initiation of a CYP1A2 inhibiting drug, such as ciprofloxacin, cimetidine, fluvoxamine, etc.

Additional medication limitations are as follows:

- Topical skin treatments to the affected NL area are not permitted during the study.
- Systemic or topical immunosuppressive therapy, including but not limited to corticosteroids (excluding intraarticular injections, inhaled or nasal steroids), calcineurin inhibitors, thalidomide, apremilast, anti-malarials (e.g., hydroxychloroquine, chloroquine), cyclosporine, mycophenolate mofetil, azathioprine, methotrexate, and biologics (TNF-α blockers, anakinra, etc.) are not permitted during the study.

- Oral retinoids are not permitted during the study.
- Phototherapy (UVA/UVB) or photochemotherapy (PUVA) is not permitted during the study.
- Consumption of pentoxifylline, cilostazol, or a theophylline preparation is not permitted during the study.

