## **2.14. Handling Missing Data**

Listings will be provided for all data. Descriptive statistics will be provided for all planned visits as provided on the Case Report Forms (CRFs). No imputations for missing data will be used in calculations.

Visit windows will not be used in this study. Likewise, unscheduled visits will not be reassigned a visit number based on the visit date.

Dates related to the medications will be imputed using the rules below in an effort to categorize them properly into the summary tables.

Imputing partial or missing start dates:

- If the year is unknown, then the start date will not be imputed. The date will remain missing.
- If the month is unknown, impute the month as January.
- If the day is unknown, impute the day as '01'.

Impute partial or missing stop dates:

- If the year is unknown, then the stop date will not be imputed. The date will remain missing.
- If the month is unknown, impute the month as December.
- If the day is unknown, impute the day to be the last day of the month.

If an imputed stop date is greater than the date of study completion/discontinuation date of the study, then the imputed stop date will be set equal to the date of completion/discontinuation date.

The imputed dates will be stored in the analysis datasets along with the original dates as recorded by the sites.

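### A response or ulcer closure that follows a graft, lesion surgery or other NL treatment can be counted as a PCS499 response, because neither document says how such visits are handled

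*Protocol*

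**What the plan says.** **Follow-up.** Protocol 12.5 says of patients whose medication is stopped: "However, patients will not be discontinued from the study due to cessation of study drug". SAP 1.2 repeats it. Protocol 10.3 adds: "The intent of this study is to follow all subjects until study termination unless the subject withdraws consent".

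**Other treatment.** The list of current NL treatments in Protocol 7.5 ends with "UV phototherapy, and skin grafting". Exclusion 4 in 10.2 rules out "Skin grafting, or other surgical procedure (other than debridement) within 6 weeks prior to Baseline". During the study, 11.2 states "Topical skin treatments to the affected NL area are not permitted during the study" and "Phototherapy (UVA/UVB) or photochemotherapy (PUVA) is not permitted during the study". It also bars systemic or topical immunosuppressives (biologics included), oral retinoids, pentoxifylline, cilostazol and theophylline. It says nothing about grafting or lesion surgery. Under 10.3, needing a prohibited medication is a ground on which a patient may be withdrawn; withdrawal is not required. Protocol 19.5.2 says "Patients withdrawn from the study will be considered evaluable for analysis".

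**Analysis.** Protocol 17.2 and 17.6 use observed data in the mITT set without imputation. SAP 2.14 summarises every planned visit. SAP 2.2 defines mITT by one dose and one post-baseline efficacy assessment. Closure (Protocol 14.1.8.1 and 16.2; SAP 2.10.8) requires re-epithelialisation with no drainage and no need for dressings, confirmed at a second visit.

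**The concern.** There is no control arm, so each by-visit proportion will be read as the effect of PCS499, and the study is meant to inform the design of later ones. If a patient has a graft, lesion surgery or another NL therapy and the lesion then improves, the plan has no rule that separates that improvement from a response to drug. With about 12 patients, and 3 to 6 in the ulcer subgroup, one such case visibly changes a reported rate. The primary objective is safety, so what is at stake is the exploratory efficacy signal.

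**Working it through.** The documents contain no sample-size, power or event-rate figure to reproduce. The check compares texts and then works out the weight of one patient.

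**1. Is each NL treatment restricted both before and during the study?**

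| Treatment | Entry (10.2) | On study (11.2) |
|---|---|---|
| Immunosuppressives, biologics | excluded | barred |
| Pentoxifylline, theophylline, cilostazol | excluded | barred |
| Phototherapy | excluded, 6 weeks | barred |
| Grafting or other surgery except debridement | excluded, 6 weeks | not mentioned |

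The phototherapy exclusion, next to exclusion 4 in the list, is carried into the study; the grafting one is not. The intralesional route for corticosteroids is in exclusion 1 and in 7.5 but is not named in 11.2.

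**2. Would a grafted ulcer meet the endpoints?**
- Closure: a healed graft can satisfy the definition, because nothing in it requires closure without surgery.
- NLCUS Ulcer: an ulcerated lesion scores 1 or 2, and a lesion with no ulcer scores 0. If the graft closes every ulcer in the reference lesion, the fall is at least 1 point.
- IGA:NL Activity: scores 0 to 3 require no ulceration, so an ulcerated lesion scores 4 or 5. Removing the ulcer allows a fall of 1 point or more unless inflammation or induration holds the score up.

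**3. Does any rule remove or mark these values?** No on-treatment restriction appears in Protocol 17 or SAP 2.10 to 2.14. The optional subgroup by completion status in Protocol 17.8 is not taken up: SAP 2.12 plans no other analyses. The SAP listings of surgical procedures and non-drug treatment are titled as history, so it is not clear that on-study procedures are captured with dates.

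**4. Weight of one patient** = 100/n.
- All patients, n = 12: 100/12 = 8.3 points.
- Ulcerated at Baseline, n = 6: 100/6 = 16.7 points; n = 3: 100/3 = 33.3 points.
- Mean percent change in ulcer area, if one ulcer goes to zero and the rest do not change: −100/6 = −16.7 to −100/3 = −33.3 points.

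**5. Chance of at least one affected patient** = 1 − (1 − q)^n, where q is an assumed per-patient rate that is not in the documents.

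| q | n = 3 | n = 6 | n = 12 |
|---|---|---|---|
| 5% | 14.3% | 26.5% | 46.0% |
| 10% | 27.1% | 46.9% | 71.8% |
| 20% | 48.8% | 73.8% | 93.1% |

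**6. Off-drug visits.** There are 8 post-baseline efficacy visits (Months 1 to 6, 9 and 12). A patient who stops drug after Month 2 could supply at most 8 − 2 = 6 of them off drug. If that patient does not enter the optional extension, the figure is 4 (Months 3 to 6).

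**7. Who stays after stopping?** Protocol 12.5 keeps patients whose drug is stopped, while 19.5.2 requires patients who refuse treatment to be discontinued from the study. Sections 9.2.2.2 (a single tablet not tolerated) and 15.1.4.1 (confirmed pregnancy) also remove patients. A patient who stops by choice could fall under either 12.5 or 19.5.2.

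**The case against.** The strongest reply is that most NL drugs are barred for the whole study, not only while PCS499 is taken, so stopping the drug does not open the way to them. This stands. What remains is grafting or surgery, and prohibited therapy used anyway.

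Keeping off-drug visits is also a recognised treatment-policy choice and fits the stated intent to follow everyone. This stands too, although the plan never says that it makes this choice. A reader might infer that off-drug visits credit another treatment to PCS499. They do not if no other treatment is given, and they may dilute a real effect.

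A reader might also infer that a grafted patient remains in the Per-Protocol set. The documents do not settle this: the protocol leaves major violations to the SAP, and SAP 2.2 and 2.8 do not define them. For the same reason the planned Per-Protocol tables are a weak safeguard.

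Exclusion 4 and 11.2 do not strictly contradict each other. One is a pre-Baseline washout and the other a concomitant-medication section, so this is an omission.

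Finally, all data are listed, deviations are summarised, and dosing changes and medications are recorded, so a careful reader could trace drug stops and prohibited drugs by patient. That helps, but it corrects no reported rate, and on-study procedures may not be traceable at all.

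**Conclusion.** The point holds as a possibility that the plan leaves open: a response or closure after a graft, lesion surgery or other NL-directed therapy can be counted as a PCS499 response. The weight is 8.3 points per patient at n = 12 and 16.7 to 33.3 points in the ulcer subgroup. These figures assume the planned numbers with all patients observed; with fewer recorded values, one patient weighs more.

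The documents do not show that such results will be credited to the drug, since they give no rate of grafting or prohibited use. The 6-of-8 count of off-drug visits is an upper bound, not an expected value. Nor does the point justify making on-drug values the main analysis. In a single arm of about 12, that would drop patients who stop for poor response or intolerance and could flatter the results. The primary safety objective is not affected.

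**What to change.** 1. **Protocol.** Reconcile exclusion 4 with 11.2 on procedures during the study, and reconcile 12.5 with 19.5.2 on whether patients who stop or refuse drug stay in. Both clinical choices are the sponsor's.
2. **SAP 2.10, response-type endpoints.** For the IGA:NL response, NLCUS-decrease and ulcer-closure endpoints, count a patient as a non-responder from the date of any graft, lesion surgery or systemic or topical NL-directed therapy. Responses before that date stand. Define lesion surgery, stating whether debridement counts (exclusion 4 leaves it out), and state how intralesional treatment is classed.
3. **Data.** Record on-study procedures with dates, or confirm that the CRF already does.
4. **Area, VAS and quality of life.** Keep the all-observed summaries as the main ones. Flag visits after drug cessation or after such therapy in the listings, and add a supportive summary that excludes them.

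The cost is SAP wording, one derived flag, one more table and possibly a CRF field, with no extra visits. Response rates may come out slightly less favourable. The rule should be fixed before results are seen, because with so few patients a case-by-case decision could itself move a reported rate.
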